The contribution of the proposed project is expected to be an evaluation of whether a quantitative postural control assessment that aligns with workflow in the clinical environment influences clinical decision making. This contribution will be significant because every patient could receive objective, quantitative postural control assessment at every office visit. Repeated measurements of postural control would create a better chance for early identification and intervention to manage balance deficits and reduce falls. It would also provide information for both providers and patients that a significant change (for better or worse) in balance status has occurred, whether due to a change in medication, neurological degeneration, an exercise intervention, or a lifestyle change.

III. Procedures

1. Research Design

This prospective, observational study uses real world data to understand whether the addition of commercially-available quantitative balance measurement informs clinical decision making by physician and advanced practice providers. A randomized crossover design will be used: Providers who enroll in the study will be randomized to receive either a scale that measures weight only, or a scale that measures balance and weight for nine months. After nine months, the scales will be switched so that every provider has the other type of scale for nine months. The first primary outcome is self-report from providers to determine if they believe the additional balance information influences their clinical decision-making within their normal clinical practice. The second primary outcome is aggregate coding and billing information for the provider over each 9-month period, to determine if diagnosis, procedure, and referral patterns by each provider differ between the two types of scale. The third, secondary outcome will be the analysis of focus-group discussions with participants to better understand their experiences in using the Balance+Weight device within their normal clinical practice.

2. Sample

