Recruitment of clinics to participate in study. Study personnel will recruit clinics to participate in an 18-month trial of the quantitative postural control assessment (Balance+Weight) device. Eligible clinics include any that self-report a substantial component of their patient population that may be at risk of falls, but that are not a referral site for patients previously identified as being at elevated falls risk. In clinics where multiple providers see patients, at least one provider must be willing to participate and commit to placing the novel device in their clinic, as well as to the other components of participation detailed below. Due to the number of ambulatory care clinics within a radius to allow same-day servicing of the devices and resource limitations to manufacture units, we will cap recruitment when we reach 20 clinics or 60 devices in service, whichever is reached first. Every participating clinic will have the opportunity to receive the device that delivers Balance+Weight either immediately or after a 9-month waiting period depending on randomization.

Randomization of clinics. A block randomization scheme by clinic type will be used to assign which clinics receive the Balance+Weight device in the first 9 months and which clinics receive the Balance+Weight device in the second 9 months. The block randomization scheme is proposed instead of simple randomization because of the expected variation between clinics in the types of patients they see. Blocks will be determined based on the estimated percent of patients seen who are over 65, diabetic, undergoing chemotherapy (all oncology clinics), or are using assistive devices during some of their care (e.g. orthopaedic trauma clinics). Clinics for whom 50% or more of their patients are in any of these categories will be included in one block, whereas clinics for whom less than 50% of their patients are in any of these categories will be included in the other block. While this scheme does not fully account for the confounder of multiple risk factors for falls or multiple co-morbidities in some clinics, equipoise between treatment arms is also achieved through the crossover design whereby every clinic serves as its own control as well.

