Training of clinics. At delivery of the Balance+Weight device to the clinic, a one-hour in-service will be performed by study personnel to train all providers and medical assistants on its proper use and the entry of data into the electronic medical record. This training will include how to operate the device and how to use the accompanying documentation with the reported data to inform clinical decision-making. This documentation will include threshold values for likelihood of the patient's balance being Within Normal Limits as well as the change in value that would indicate a change in the patient's balance status along with appendices that contain the published peer-reviewed journal articles upon which these recommendations are based. Upon request by the clinic, study personnel will repeat the training if refreshers are needed by clinic staff. An unlimited number of refresher trainings are permitted for each clinic, and the number of trainings requested per clinic will be recorded.

Incorporation of quantitative postural control assessment device into clinic flow including immediate feedback on clinical utility. Each participating clinic will place the study device in a location to allow its use instead of their weight scale. In the Balance+Weight arm, the device is capable of either just giving weight, or of providing balance data if the patient stands quietly with eyes closed for 30s. In the Weight Only arm, the device only gives a weight measurement, just as a standard weight scale would. In both

cases, the provider and their staff make their own clinical decisions as to which patients to make measurements of and how to use the provided information. The medical assistant may choose to enter the appropriate values into the medical record and continue with any other standard procedures in that clinic setting as part of the rooming or initial evaluation process. The provider can then examine the recorded balance measurement along with their standard examination and determine whether any further evaluations in that clinic or referral to a specialist, physical therapy, or other falls prevention is appropriate and record that diagnosis or referral into the medical record.

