Immediate feedback from provider on clinical decision-making process. After each patient encounter in which the provider assessed balance using the Balance+Weight device, the provider who made a clinical decision regarding balance or falls risk is asked to press a button on a small kiosk that we will provide which logs their agreement with the statement, "The balance measurement influenced my clinical decision making with this patient." These kiosks from Happy-Or-Not.com are completely wireless and use their own 3G network to communicate the results of a single 4-point Likert scale question back to a central server that the study staff can monitor to collect data and get a real-time indication of whether the providers are using the Balance+Weight device.

Crossover of sites after 9 months. At the 9-month point, study personnel will go to every site to reprogram each device from Balance+Weight mode to Weight Only mode or vice versa, and to move the immediate feedback kiosks to the new Balance+Weight sites.

Data pull of clinic-level diagnosis and referral data. At or just after the crossover between sites has occurred, study personnel in conjunction with the IT departments at participating sites will pull the clinic diagnosis and referral data for all participating providers. After Casey et al.[15], our initial plan is to count instances of the following Common Procedural Terminology Category II codes:

- (Primary) CPT II 3288: Assessment of falls risk
- CPT II 0518: Development of a falls care plan
- CPT II 1101: Documentation of falls in past year (no falls/ single fall without injury)
- CPT II 1100: Documentation of an injurious fall/ multiple falls
- Other referral codes as appropriate

Because CPT codes are updated each calendar year, we will review the new codes each year and revise this code list as new codes related to falls assessment are added or subtracted. We will pull this data from both the 9 months of participation in the study, as well as the same 9 month period in the calendar year before the study began as a historical control. The data will be pulled again upon completion of the study for the second 9-month period.

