Statistical analysis of clinical billing data. Counts of each code listed above will be tabulated for each provider during the 9 month period in the year before beginning the trial, during the 9 months with the Balance+Weight device, and during the 9 months with the Weight Only device; normalized by the total patient encounters by that provider over the same time periods to get incidence rates of each code for each condition (historical, Balance+Weight, Weight Only). The incidence rate ratios of Balance+Weight to the other two conditions will then be calculated, and the 95% confidence intervals of those incidence rate ratios will be calculated to see which are significantly different from 1.0, as we have previously done with other epidemiological data [16]. Each code is considered separately, because it is possible that multiple codes may be used in a single encounter, but as the primary goal of a quantitative postural control assessment is to trigger further action by the provider to confirm that the individual has a balance impairment, the primary variable of interest is CPT II 3288: Assessment of falls risk. This approach would statistically test the hypothesis that the provider is more likely to proceed in any falls risk algorithm such as STEADI on to a further assessment of falls risk with quantitative postural control information in addition to patient self-report or clinical observation. Using the data reported by Casey et al. in their implementation of STEADI [15], where they reported an initial rate of an assessment of falls risk of 19% across 16 providers over 3 months leading to 360 screens, we estimate that with 10 providers in each group over 9 months there could be approximately 3552 patient encounters in each group, or 7105 patient encounters over 18 months. With this number of patient encounters, we would have sufficient power to detect an incidence rate ratio of 1.1, or a 10% increase in Assessments of falls risk. Given the reported rate from Casey et al. that 35% of assessed patients score as high risk, that 10% increase could lead to approximately 47 additional high-risk individuals being identified, which we deem a clinically significant improvement.

IV. List of References

1. World Health Organization. WHO Global Report on Falls Prevention in Older Age.; 2007. doi:978 92 4 156353 6.

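### The crossover has no washout and no carryover check, so any lasting effect of the Balance+Weight training would pull the Balance+Weight vs Weight Only billing ratio toward 1

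*Combined protocol and SAP*

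**What the plan says.** **Switch.** Section III.1 (Research Design) sets two nine-month periods: "After nine months, the scales will be switched so that every provider has the other type of scale for nine months". Under Crossover of sites in III.4, the only actions at the switch are to "reprogram each device from Balance+Weight mode to Weight Only mode or vice versa" and to move the feedback kiosks. No washout, run-in or excluded interval is mentioned.

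**What the clinic receives with Balance+Weight.** Training of clinics (III.4) says that, when the Balance+Weight device is delivered, "a one-hour in-service will be performed by study personnel to train all providers and medical assistants on its proper use". The content goes beyond operation: "This training will include how to operate the device and how to use the accompanying documentation with the reported data to inform clinical decision-making". On the written material: "This documentation will include threshold values for likelihood of the patient's balance being Within Normal Limits". It also covers the change in value that would signal a changed balance status, and includes the supporting articles. Refresher sessions are unlimited. Nothing withdraws any of this at the switch.

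**Reliance on the crossover.** Randomization of clinics (III.4) answers residual imbalance by noting that "every clinic serves as its own control as well". Internal Validity (III.5) makes the same appeal. Neither mentions carryover.

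**Analysis.** In III.6 (Statistical analysis of clinical billing data), code counts are tabulated per provider for the historical nine months, "during the 9 months with the Balance+Weight device, and during the 9 months with the Weight Only device", and divided by encounters. Balance+Weight is then compared with Weight Only and with the historical period. There is no period, sequence or carryover element, no first-period analysis, and no Weight Only vs historical contrast.

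**The concern.** By design, Weight Only is two different conditions. In clinics randomized to Weight Only first, staff have not yet had the Balance+Weight training. In clinics randomized to Balance+Weight first, staff have been trained, hold the thresholds and have had up to nine months of use. The analysis treats both as the same control.

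Carryover is plausible on the plan's own reasoning. The Background names providers' lack of knowledge about falls assessment as a barrier, and the Balance+Weight package partly addresses that barrier. The primary code, CPT II 3288, records an assessment that can be done without the device, so a provider who has learned to assess falls risk can keep doing so on a weight-only scale.

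If that happens, the Weight Only rate rises in half the control time and the ratio moves toward 1. A result near 1 could then mean no device effect, or a device effect that outlasted the switch. As written, the plan contains no analysis aimed at telling these apart.

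**Working it through.** **Step 1. Reproduce the plan's figures (III.6).** Inputs: 360 screens, a 19% rate, 16 providers, 3 months.
- Encounters for 10 providers over 9 months: 360 / 0.19 / 16 / 3 × 10 × 9 = 3552.6 (plan: 3552).
- Over 18 months: 2 × 3552.6 = 7105.3 (plan: 7105).
- Extra high-risk patients: 7105 × 0.19 × 0.10 × 0.35 = 47.2 (plan: 47).

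The figure of 47 uses 7105 encounters, that is, both periods combined. The plan claims sufficient power for a ratio of 1.1 but gives no percentage.

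**Step 2. Dilution.** Let R be the true ratio and c the share of the effect that persists in Weight Only months following Balance+Weight. Assume equal encounters in the two sequences and no period effect. Half the Weight Only time then runs at 1 + c(R − 1) times the base rate, so

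expected ratio = R / [1 + 0.5c(R − 1)] = 1.10 / (1 + 0.05c) for R = 1.10.

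**Step 3. Power**, two-sided 5%, 7105 encounters per condition.
- Poisson: Φ(ln(ratio)/SE − 1.96), with SE = √(1/e₀ + 1/e₁). Here e₁ = 7105 × 0.209 ≈ 1485 and e₀ = 1350 × (1 + 0.05c).
- Proportions: 0.209 against 0.19 × (1 + 0.05c).

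| c (assumed) | e₀ | Expected ratio | Power, Poisson | Power, proportions |
|---|---|---|---|---|
| 0 | 1350 | 1.100 | 72% | 81% |
| 0.5 | 1384 | 1.073 | 47% | 56% |
| 1 | 1418 | 1.048 | 24% | 29% |

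For example, at c = 0.5: ln 1.0732 = 0.0706, SE = 0.0374, 0.0706/0.0374 − 1.96 = −0.07, power 47%.

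**Step 4. What a split by sequence would show.** In Balance+Weight-first clinics the expected ratio is 1.10 / (1 + 0.10c): 1.048 at c = 0.5 and 1.000 at c = 1. In Weight-Only-first clinics it stays at 1.10.

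**Step 5. First period only.** This comparison has no carryover. With about 675 control and 742.5 Balance+Weight events, SE = √(1/675 + 1/742.5) = 0.0532, and power at 1.10 is 43% (Poisson) or 52% (proportions). Both ignore variation between clinics. Suppose a residual between-clinic coefficient of variation of 0.1 to 0.3 after adjustment for history (my assumption; the documents give none). The variance is then 0.0532² + 2 × CV²/10, and Poisson power falls to about 28% at 0.1 and 10% at 0.3.

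So 80% power for 1.10 is reached only by combining both periods and only on the proportions calculation. The power claim therefore depends on the combination that carryover would distort.

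**The case against.** **The documents do not show that carryover will occur.** This stands. The training is about using the device's readings, and thresholds for a reading no longer produced have limited use in Weight Only months. Persistence of 100% over nine months is an extreme bound. The plan is exposed to a bias it does not check; a reader should not infer that the ratio is biased as a matter of fact.

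**Recorded readings.** A reader might also infer that earlier balance values will be on file and guide later decisions. The plan leaves their entry to the medical assistant's choice, so persistence of readings is possible but not established. The argument rests on the training and documentation.

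**There is a second comparator.** The plan also compares Balance+Weight with the historical period, which precedes all training. It would be wrong to say that the trial reports a single ratio with nothing to set against it. Period-specific data are pulled too, so sequence-specific rates can be recovered. But the historical ratio is open to secular trend, and no Weight Only vs historical or by-sequence contrast is specified.

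**Depletion.** A reader might infer the opposite bias: patients assessed in period 1 are not coded again in period 2, which inflates the ratio even if the device does nothing. This does not follow. With no device effect, both sequences are depleted equally. At an assumed 10%, the ratio is (1 + 0.9)/(1 + 0.9) = 1.00, a period effect that a balanced crossover cancels. With a true 1.10 and depletion proportional to earlier assessments (10% and 11%), it is (1.10 + 1.10 × 0.90)/(1 + 0.89) = 1.106, a negligible shift.

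**The bias is conservative.** If carryover raises assessments, it does not create a false positive. But it would understate a co-primary result and could make a null finding uninterpretable.

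**Conclusion.** The concern holds for one quantity: the Balance+Weight vs Weight Only billing ratio. The switch has no washout, the training is irreversible, Weight Only months from both sequences are combined, and no check is planned. If part of the effect persists, a true 1.10 is expected to appear as something between 1.100 and 1.048, with power falling from 72% to 24% (Poisson) or from 81% to 29% (proportions).

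This rests on an assumed persistence of 0% to 100%, equal encounters by sequence, no period effect, and no allowance for clustering by clinic or pairing within clinic, for which the documents give no inputs. It also reads the training as given when a clinic starts Balance+Weight, not when a unit arrives in Weight Only mode. Whether ratios are formed per provider or from combined counts does not matter, since the trained clinics' control months enter either way.

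The kiosk outcome is not affected, because it is collected only under Balance+Weight. The remedy is a cheap improvement to the analysis text and does not call for a redesign.

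**What to change.** Keep the crossover estimate as primary. Add to the billing analysis in III.6, for CPT II 3288:

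- **(a) Descriptive carryover checks.** Report the Balance+Weight vs Weight Only ratio by sequence, and the Weight Only vs historical ratio by sequence.
- **(b) A pre-specified first-period sensitivity analysis.** Compare Balance+Weight-first with Weight-Only-first clinics in period 1 only, adjusted for each clinic's historical rate, with clinic-level standard errors.
- **(c) Reporting rule.** Present all estimates side by side with 95% confidence intervals, and use none of the checks to choose the primary analysis. State in advance that a primary ratio near 1 will not be read as no device effect if the Weight Only rate relative to historical is higher in the Balance+Weight-first clinics.

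The cost is a few lines of text and no new data, since the historical and period-specific counts are already to be pulled. There are two limits to state openly. The checks compare about 10 clinics with 10: the first-period analysis has at most about 43% Poisson power at 1.10, and less once between-clinic variation is counted. The checks in (a) also mix carryover with calendar change, because Weight Only falls in different periods in the two sequences. Only (b) compares clinics over the same months. Together they limit what may be concluded; they cannot prove that carryover is absent.

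### Study-period billing data are extracted as each period closes, but the historical window is about a year old, so the Balance+Weight to historical ratio may be biased downward if falls-risk codes post later than encounters are counted

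*Combined protocol and SAP*

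**What the plan says.** Sections III.3 and III.4 of the combined protocol and SAP describe two extracts. The first is made "At or just after the crossover between sites has occurred" and covers the first study period and "the same 9 month period in the calendar year before the study began as a historical control". For the other period, III.4 says: "The data will be pulled again upon completion of the study for the second 9-month period". Neither section gives a run-out interval, a freeze date, a rule for selecting by date of service, or a repeat extract of the first period.

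Section III.6 (clinical billing data) turns code counts into rates, "normalized by the total patient encounters by that provider over the same time periods". It does not name the source of the encounter count. It continues: "The incidence rate ratios of Balance+Weight to the other two conditions will then be calculated". Each ratio is judged by whether its 95% confidence interval excludes 1.0, and "the primary variable of interest is CPT II 3288: Assessment of falls risk".

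**The concern.** The three conditions are read at different maturity. The historical window has had about twelve months for late entries to arrive. Each study window has had little or no time.

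If encounters register at the visit and the falls-risk code is posted later, the study-period numerator is cut and its denominator is not. The historical rate is unaffected, so the Balance+Weight to historical ratio is pushed down. The plan's target is only a 10% increase, so a loss of a few per cent of codes would matter.

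The planned analysis would not expose the problem. Weight Only to historical, where the same artefact would appear as a shortfall without the device, is not among the ratios to be calculated.

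**Working it through.** **Plan's own figures (III.6).** The source is "an initial rate of an assessment of falls risk of 19% across 16 providers over 3 months leading to 360 screens". The encounters implied are 360 / 0.19 = 1894.7. Per provider-month this is 1894.7 / (16 × 3) = 39.47. Ten providers over nine months give 39.47 × 10 × 9 = 3552.6, and twice that is 7105.3. This reproduces "approximately 3552 patient encounters in each group, or 7105 patient encounters over 18 months". These figures only set the scale; the target is a ratio of 1.1.

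**Inputs not in the documents (assumptions).** Encounters are spread evenly over a window of T = 0.75 × 365.25 / 7 = 39.13 weeks. Posting lag is exponential with mean m weeks. The extract is made r weeks after the window closes.

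**Formulas.**
- Share of codes missing: f = (m/T) × [exp(−r/m) − exp(−(T + r)/m)], which is about m/T when r = 0.
- Observed ratio to historical = true ratio × (1 − share of codes missing) / (1 − share of encounters missing).

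**Results with complete encounter counts and a true ratio of 1.10.**

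| Mean lag (weeks) | Codes missing, r = 0 | Observed ratio, r = 0 | Observed ratio, r = 2 | Codes missing, r = 13 | Observed ratio, r = 13 |
|---|---|---|---|---|---|
| 1 | 2.6% | 1.07 | 1.10 | <0.1% | 1.10 |
| 2 | 5.1% | 1.04 | 1.08 | <0.1% | 1.10 |
| 4 | 10.2% | 0.99 | 1.03 | 0.4% | 1.10 |

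Example for m = 4, r = 0: 4 / 39.13 = 10.2%, and 1.10 × (1 − 0.102) = 0.99. For m = 4, r = 2: 0.1022 × exp(−0.5) = 6.2%, and 1.10 × 0.938 = 1.03.

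**Loss that cancels the target.** 1 − 1/1.1 = 9.1% of codes, a mean lag of 0.091 × 39.13 = about 3.6 weeks.

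**Equal lag in codes and encounters.** The two missing shares are the same, the fraction equals 1, and the bias is zero at every lag.

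**Effect on the test against historical.** Power is Φ[ln(IRR) / √(1/(0.19n) + 1/(0.19n × IRR)) − 1.96]. Take n = 7105 per condition, as when all 20 clinics give nine months to each. Power is 72% with no loss, and 45%, 20% and 1% at mean lags of 1, 2 and 4 weeks. This treats counts as independent Poisson and ignores clustering by clinic, so it is illustrative only.

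**Randomized ratio.** Let the two periods lose shares f1 and f2, and let R be the true Balance+Weight to Weight Only ratio. Clinics with the device first show R(1 − f1)/(1 − f2); clinics with it second show R(1 − f2)/(1 − f1). If f1 = f2, each equals R. If they differ, the product is R², so the geometric mean is R. Pooled counts also give R when the two sequences have equal volume.

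**The case against.** The strongest reply is that nothing in the documents shows a lag. They do not mention late posting, late entry of these codes, or separate systems for codes and encounters. Section III.4 has providers recording diagnoses and referrals in the medical record, and the extract is run with clinic IT departments, so both counts might come from the same records and lag together. The wording also allows a short wait, and the table shows how quickly even two weeks reduces the loss. All of this stands, and it makes the point a conditional one. However, the plan calls these billing data, sets no minimum wait and does not name the denominator source, so it cannot claim that protection.

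It can also be said that the exposed ratio is the non-randomized one and that the bias would not create a false claim of benefit. That is right for a benefit claim. But III.6 does test this ratio against 1.0, and with no true effect the assumed lags would give about 0.97, 0.95 or 0.90, which could be read as a reduction.

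Two stronger readings are tempting and fail:
- A reader might infer that late codes are lost for good because the data are de-identified aggregates. They are not: an aggregate count by date window can be queried again.
- A reader might infer that unequal delays at the two extracts damage the randomized comparison. A difference between extracts acts as a period effect. Section III.4 randomizes clinics to both orders, so each condition draws on both periods and the effect largely balances.

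**Conclusion.** The difference in maturity is stated in the plan, and no run-out is specified. Whether it biases the Balance+Weight to historical ratio depends on three conditions that the documents leave open: a material posting lag, an extract at or very near closing day, and encounters counted sooner than codes. If all three hold, the direction is downward. At assumed mean lags of 1 to 4 weeks the loss is 2.6% to 10.2% of codes, which ranges from a quarter of the 10% target effect to all of it. If codes and encounters lag equally, the bias is nil.

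The documents do not support saying that codes are missing or that the ratio is biased. They support saying that the schedule permits it and that the planned ratios would not show it. The randomized Balance+Weight to Weight Only ratio is largely protected, with small departures possible if extract delays differ and the two sequences are unequal in volume.

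**What to change.** In III.3 and III.4, specify that at the final extract the historical window and both study periods are extracted again together. Select by date of service, after a common fixed run-out following the second period (for example 90 days, about 13 weeks). Take code counts and encounter counts from that same extract, and state this in III.6. The month-9 extract can stay as an interim check of the query. Under the assumptions above, a 13-week run-out leaves at most 0.4% of codes missing for mean lags up to 4 weeks. At a mean lag of 8 weeks about 4.0% would still be missing (ratio 1.06), against 20.3% (ratio 0.88) at a closing-day extract.

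The cost is one added re-query with the IT departments of up to 20 clinics, and a final analysis delayed by the run-out. No patients, visits or devices are added.
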